1. INTRODUCTION

The purpose of this reporting and analysis plan (RAP) is to describe the analyses to be included in the Clinical Study Report for Protocol of study 207972 (GSK Document No.: 2017N331706_03).

Revision Chronology:		
2017N331706_00	01-SEP-2017	Original
2017N331706_01	05-FEB-2018	
Clarified that participants with severe asthma for whom it is felt oral corticosteroids are warranted are not eligible for this study.
 
Clarified the use of anti-fungal medication throughout the study.
 
Clarified the run-in and randomisation criteria sections.
 
Clarified the timing of contraceptive requirements for female participants.
 
Provided a definition for former smokers.
 
Removed the body temperature in the objectives and safety analyses and updated Section 9 to reflect that body temperature will be collected but only available in source documents.
 
Corrected formatting and typographical errors.

2017N331706_02	26-JUL-2018	Russia specific: To allow Russian Federation Sites to conduct the screening assessments over 2 separate visits.
2017N331706_03	10-OCT-2018	To include participants with severe asthma with AFAD treated with low dose oral corticosteroid who still demonstrate a lack of complete control as demonstrated by ACQ-5, FeNO and blood eosinophil levels. Also, a few clarifications were included.
2017N331706_04	10-OCT-2018	Russia specific: To include participants with severe asthma with AFAD treated with low dose oral corticosteroid who still demonstrate a lack of complete control as demonstrated by ACQ-5, FeNO and blood eosinophil levels. Also, a few clarifications were included.

2. SUMMARY OF KEY PROTOCOL INFORMATION

2.1. Changes to the Protocol Defined Statistical Analysis Plan

Changes from the originally planned statistical analysis specified in the protocol are outlined in [Table 1](#).

Table 1 Changes to Protocol Defined Analysis Plan

Protocol	Reporting & Analysis Plan	
Statistical Analysis Plan	Statistical Analysis Plan	Rationale for Changes
Primary and secondary endpoints to be analysed.	All endpoints to be summarised only.	Enrolment into the 207972 study was terminated early due to the

[figure not shown]
Protocol	Reporting & Analysis Plan	
Statistical Analysis Plan	Statistical Analysis Plan	Rationale for Changes
		feasibility of completing the study in a timely manner, resulting in insufficient subjects for analysis to be performed.
An internal Safety Review Committee (iSRC) was to review safety data after the 20 th randomised subject received their first post-dose ECG/24hr Holter. A potential interim analysis, end of treatment analysis and final SAC analysis was due to be performed.	No iSRC analysis and only one final SAC analysis to be performed.	The study was unable to recruit the 20 randomised subjects required for the iSRC prior to termination. In addition, as recruitment was terminated early, and would not inform internal decision making, there was no requirement to report at multiple timepoints to align with portfolio decisions.
Primary, secondary and exploratory endpoints to be reported.	Primary and secondary endpoints only to be reported.	As there is insufficient data to draw any conclusions on exploratory endpoints, and they are not required for external disclosure, no outputs will be created.

2.2. Study Objective(s) and Endpoint(s)

Objectives	Endpoints
Primary Objectives	Primary Endpoints
To evaluate the efficacy of 3 doses of GSK3772847 (administered every 4 weeks) compared with placebo in moderate to severe asthma participants with allergic fungal airway disease (AFAD) who are currently on Standard of Care (SoC)	
 Change from baseline (Week 0) in blood eosinophils over time Change from baseline (Week 0) in fractional exhaled nitric oxide (FeNO) over time
Secondary Objectives	Secondary Endpoints
To evaluate the serum pharmacokinetics (PK) of 3 doses of GSK3772847 (administered every 4 weeks) in moderate to severe asthma participants with AFAD	
 Serum concentrations of GSK3772847
To evaluate the pharmacodynamics (PD) of GSK3772847 in moderate to severe asthma participants with AFAD	
 Serum levels of free and total soluble suppressor of tumorigenicity 2 (sST2)
To evaluate the levels and specificity of any anti-drug antibodies formed following dosing with GSK3772847	
 Incidence and titres of serum anti- GSK3772847 antibodies
To evaluate the health status of moderate to severe asthma participants with AFAD currently on SoC, and who are treated with GSK3772847 compared with placebo-treated participants	
 Change from baseline (Week 0) in Asthma Control Questionnaire -5 (ACQ-5) absolute score at Weeks 2, 4, 8 and 12 Change from baseline (Week 0) in Asthma Quality of Life Questionnaire (AQLQ) total and domain scores at Weeks 2, 4, 8 and 12 Proportion of responders to ACQ-5. A responder to

Objectives	Endpoints
	
ACQ-5 will be defined as a subject who has a decrease from baseline in ACQ-5 score of 0.5 or more at Weeks 2, 4, 8 and 12.
 
 • Proportion of responders to AQLQ. A responder to AQLQ will be defined as a subject who has an increase from baseline in AQLQ score of 0.5 or more at Weeks 2, 4, 8 and 12.
To evaluate the effect on lung function of moderate to severe asthma participants with AFAD currently on SoC, treated with GSK3772847 compared with placebo	
 • Change from baseline (Week 0) in spirometry parameters over time including but not limited to pre-bronchodilator Forced expiratory volume in 1 second (FEV1).
To evaluate the safety and tolerability of GSK3772847 compared with placebo in moderate to severe asthma participants with AFAD	
Safety and tolerability parameters include:
 
 • Treatment emergent adverse events (AE) • Clinical Laboratory safety data • Vital signs (blood pressure, heart rate) • 12-Lead Electrocardiogram (ECG) monitoring • 24-hour Holter monitoring
Exploratory Objectives	Exploratory Endpoints
To evaluate changes in exploratory biomarkers in the blood of moderate to severe asthma participants with AFAD who have been treated with GSK3772847 compared with placebo	
 • Change over time in levels of serum total Immunoglobulin E (IgE), fungal-specific IgE
To evaluate changes in IL-33 related and disease biology biomarkers in the sputum of moderate to severe asthma participants with AFAD who have been treated with GSK3772847 compared with placebo	
 • Difference from placebo in levels of sputum biomarkers including but not limited to interleukin (IL)-33, IL-13, IL-4, IL-5 and TNF- α • Difference from placebo including but not limited to levels of sputum eosinophils

2.3. Study Design

2.4. Statistical Analyses

Due to the study being terminated early, there were insufficient subjects to enable the planned statistical analysis to be performed. As a result, all data will be summarised descriptively only.

3. PLANNED ANALYSES

3.1. Final Analyses

The final planned analyses will be performed after the completion of the following sequential steps:

1. All participants have completed the study as defined in the protocol
2. All required database cleaning activities have been completed and database release has been declared by Data Management.
3. All criteria for unblinding the randomisation codes have been met.
4. Randomisation codes have been distributed according to RandAll NG procedures.
5. Database freeze (DBF) has been declared by Data Management.

4. ANALYSIS POPULATIONS

4.1. Analysis Populations

Population	Definition / Criteria	Analyses Evaluated
Enrolled	The All Subjects Enrolled (ASE) population will consist of all participants who sign the ICF.	
 • Study population • Subjects by country and site ID • Age ranges • Screening/run-in status and reason for screening/run-in failure.
Screened	The screened population will consist of all participants who sign the ICF, but who did not pass the screening/run-in criteria and therefore were not randomised.	
 • Reasons for screen/run-in failure
Randomised	The randomised population will consist of all participants who were randomised. A participant who is recorded as a screen or run-in failure and also randomised will be considered to be randomised in error provided they have not performed any study assessments.	
 • No formal analysis will be performed on this population
Modified Intent-to-Treat	
 • The modified Intent-to-Treat (mITT) will consist of all randomised participants who take at least 1 dose of study treatment. • Participants will be analysed according to the treatment they receive $\geq 50\%$ of the time. If the participant receives 50% of each treatment they will be analysed according to the randomised treatment. 	
 • Study population • Inclusion, exclusion and randomisation criteria deviations • Participant disposition • Efficacy

Population	Definition / Criteria	Analyses Evaluated
Safety	This population will be the same as the Modified Intent-to-Treat population.	
 • Safety
Pharmacokinetic	The PK population will consist of all randomised participants who received at least one dose of study medication, and for whom at least one pharmacokinetic sample was obtained, analysed and was measurable.	
 • PK

Refer to [Appendix 10](#): List of Data Displays which details the population used for each display.

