7.1. Primary Efficacy Analyses

7.1.1. Endpoints and Summary Measures

Primary Endpoints	Summary Measure
Change from baseline (Week 0) in blood eosinophils over time	Summary statistics (raw and change from baseline)
Change from baseline (Week 0) in fractional exhaled nitric oxide over time	Summary statistics (raw and change from baseline)

Primary efficacy summaries will be based on the mITT population and no intercurrent events will be considered.

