7.2. Secondary Efficacy Analyses

7.2.1. Endpoint and Summary Measure

Secondary Endpoints	Summary Measure

 Change from baseline (Week 0) in spirometry parameters over time including but not limited to pre-bronchodilator Forced expiratory volume in 1 second. Change from baseline (Week 0) in Asthma Control Questionnaire -5 absolute score at Weeks 2, 4, 8 and 12 Change from baseline (Week 0) in Asthma Quality of Life Questionnaire total and domain scores at Weeks 2, 4, 8 and 12 	Summary statistics (raw and change from baseline)

 Proportion of responders to ACQ-5. A responder to ACQ-5 will be defined as a subject who has a decrease from baseline in ACQ-5 score of 0.5 or more at Weeks 2, 4, 8 and 12. Proportion of responders to AQLQ. A responder to AQLQ will be defined as a subject who has an increase from baseline in AQLQ score of 0.5 or more at Weeks 2, 4, 8 and 12. 	Number and percentage of responders

Secondary efficacy summaries will be based on the mITT population and no intercurrent events will be considered.

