12.6.2. Study Population

Age
Date of birth will be set as 30-JUN-YYYY where YYYY is the year of birth taken from the CRF. For participants who attended a screening visit, age will be calculated at the screening visit date.
Body Mass Index (BMI)
$BMI = \text{Weight (kg)} / \text{Height(m)}^2$
Treatment Misallocations
To allocate treatment, the number of doses of GSK3772847 and Placebo that were given will be calculated, and the subject will be assigned to whichever treatment has the higher number. The only exception will be when both treatments were given equally, in which case the subject will be assigned their randomised treatment.
Extent of Exposure (Therapeutic Coverage)

 • IP is administered approximately every 4 weeks and each dose viewed as providing therapeutic coverage for 4 weeks (28 days). • Number of days of exposure to study drug will be calculated based on the formula: Duration of Exposure in Days = Study Treatment Last Dose Date – (Study Treatment First Dose Date) + 29 • The only exception to this will be when a participant dies in which case Duration of Exposure in Days = Death Date – (Study Treatment First Dose Date) + 1

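### One majority-of-doses rule sets the treatment column for both efficacy and safety, so a misallocated participant could leave the randomised arm or have active exposure shown under placebo (minor)

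*SAP*

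**What the plan says.** Section 4.1 of the SAP defines the mITT population by membership and by grouping. On membership, it "will consist of all randomised participants who take at least 1 dose of study treatment". On grouping, "Participants will be analysed according to the treatment they receive" at least 50% of the time, and "If the participant receives 50% of each treatment they will be analysed according to the randomised treatment".

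Section 12.6.2, under Treatment Misallocations, turns this into a count of doses: "the subject will be assigned to whichever treatment has the higher number", except when the two counts are equal, "in which case the subject will be assigned their randomised treatment".

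For the Safety population, section 4.1 says only "This population will be the same as the Modified Intent-to-Treat population". No other section gives safety displays a different treatment assignment.

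The efficacy displays rest on the same grouping: "Primary efficacy summaries will be based on the mITT population" (section 7.1.1) and "Secondary efficacy summaries will be based on the mITT population" (section 7.2.1). Section 4.1 plans no formal analysis of the Randomised population, so the SAP has no efficacy display by randomised arm.

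**The concern.** Efficacy and safety usually need different treatment assignments when dosing errors occur.

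- **Efficacy.** The name mITT suggests that participants stay in the arm to which they were randomised. Here they are placed by what they mostly received, which is an as-treated grouping. The column can also depend on when dosing stops. Take a participant randomised to GSK3772847 who is given placebo at the first dose. If dosing ends there, the participant is shown as placebo. If the second and last dose is active, the tie rule moves the participant back to GSK3772847.
- **Safety.** The usual aim is that exposure to active drug is not hidden in the comparator column. A majority rule can do exactly that: events, vital signs, ECG and laboratory changes after a single active infusion would be counted under placebo if placebo doses are in the majority.

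Both matter because section 2.2 frames the primary efficacy objective and the safety objective as comparisons with placebo.

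**Working it through.** The SAP gives no figure of its own to reproduce. The check applies the stated rule to every possible dosing history.

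**Inputs**
- Planned doses per participant: 3 (section 2.2). Participants who stop early may have 1 or 2.
- Rule: the treatment with more doses wins, and a tie goes to the randomised arm (sections 4.1 and 12.6.2).
- Safety uses the same assignment as mITT (section 4.1).
- Number randomised: fewer than 20. Section 2.1 says that the 20 randomised participants needed for the internal safety review were not reached.

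**Enumeration.** Write G for an active dose and P for a placebo dose. With n doses and two randomised arms there are 2 × 2^n combinations of arm and dose sequence. These are possible histories and not probabilities.

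| Doses received | Combinations | Shown outside the randomised arm | At least one active dose but shown as placebo |
|---|---|---|---|
| 1 | 2 × 2 = 4 | 2 | 0 |
| 2 | 2 × 4 = 8 | 2 | 2 |
| 3 | 2 × 8 = 16 | 8 | 6 |

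**Efficacy column, three doses.** A participant randomised to placebo with 2 or 3 active doses moves to GSK3772847 (GGP, GPG, PGG, GGG: 4). A participant randomised to active with 2 or 3 placebo doses moves to placebo (GPP, PGP, PPG, PPP: 4). Total 4 + 4 = 8.

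**Safety column, three doses.** Exactly one active dose gives GPP, PGP or PPG, in either arm: 3 × 2 = 6.

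**Safety column, two doses.** GP and PG are ties. They go to placebo only if the participant was randomised to placebo: 2.

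**An example.** In the schedule of activities (section 12.2.1) the 24-hour Holter is recorded at run-in and at Week 0 only. With sequence GPP, the only post-dose Holter, recorded after an active infusion, would count under placebo in Table 3.09.

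**With the two functions separated.** If efficacy is grouped as randomised, the third column of the table becomes 0 in every row. If safety shows any active dose under GSK3772847, the fourth column becomes 0 in every row.

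**Weight of one participant.** With at most 19 randomised, 1/19 = 5.3%, so at least about 5% of the trial. The SAP gives neither arm sizes nor the allocation ratio. If 19 were split 9 and 10 (an assumption), one participant would be 1/10 = 10% to 1/9 = 11% of an arm.

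**The case against.** The case against giving this much weight is strong, and most of it stands.

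- **No inference is planned.** Sections 2.1, 2.4 and 7 restrict the report to descriptive summaries. A reader might infer that the rule breaks randomisation and biases the treatment comparison. The SAP does not support that: no estimate of effect, interval or test is planned. The most that can happen is that a column of descriptive statistics does not match the randomised arm.
- **It depends on a misallocation.** A reader might also infer that one happened. The SAP does not say so. The safety part is narrower still, because it needs a participant who received both treatments. Someone given only active drug is already shown under GSK3772847, whichever arm was allocated.
- **The rule is explicit.** Sections 4.1 and 12.6.2 agree with each other and cover ties. This is not a contradiction or an ambiguity.
- **A case would be traceable.** Listing 5 (randomised and actual treatment), Listing 12 (exposure) and Listing 13 (adverse events) would let a reader reconstruct it.
- **The any-active-dose rule is imperfect too.** For sequence PPG, events before the third dose would appear under GSK3772847. No single column attributes mixed dosing correctly.

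The rule itself remains open to criticism. Listings do not correct the tables. The tie rule does not remove the safety problem and extends it to a placebo-randomised participant with one dose of each. Showing some pre-exposure events under active is also the more cautious error in a safety table.

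**Conclusion.** The point holds as a minor one. The grouping does not match the mITT name, and the Safety population inherits a rule that can place a participant with a minority of active doses under placebo, or one with half if randomised to placebo. The conclusion rests on two conditions: that at least one participant received a treatment other than the allocated one, and, for safety, that the participant received both treatments. If neither occurred, every table is unchanged. If one did, the participant is at least about 5% of the trial, which can visibly shift a descriptive mean or an adverse event percentage. Any figure for the share of an arm needs an assumed arm size. The 5% is one person's weight, not an estimate of bias.

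**What to change.** In sections 4.1 and 12.6.2, separate the two functions now served by one rule.

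1. Summarise the mITT efficacy tables (2.02 to 2.08) by randomised treatment.
2. Keep the membership of the Safety population as it is, but give it its own actual-treatment variable: any participant with at least one active dose is shown under GSK3772847.
3. Footnote any mixed-dosing participant in the safety tables, with a reference to Listings 5 and 12. The footnote should say that events before the first active dose also appear under GSK3772847.

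The cost is a few lines of SAP text and one more treatment variable in the analysis datasets. The planned footnote to Table 1.09 that Safety and mITT are the same stays true for membership and needs a qualifier for treatment assignment. If no participant was misallocated, no result changes.

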4.2. Protocol Deviations

Important protocol deviations (including deviations related to study inclusion/exclusion criteria, conduct of the trial, patient management or patient assessment) will be summarised and listed.

Protocol deviations will be tracked by the study team throughout the conduct of the study in accordance with the Protocol Deviation Management Plan [Version 2 (19-JUN-2018) or higher].

- Data will be reviewed prior to unblinding and freezing the database, to ensure all important deviations are captured and categorised on the protocol deviations dataset.
- This dataset will be the basis for the summaries and listings of protocol deviations.

A separate summary and listing of all inclusion/exclusion criteria deviations will also be provided. This summary will be based on data as recorded on the inclusion/exclusion page of the eCRF.

Note: Inclusion and exclusion criteria deviations are always reported as important.

5. CONSIDERATIONS FOR DATA ANALYSES AND DATA HANDLING CONVENTIONS

5.1. Study Treatment & Sub-group Display Descriptors

Treatment Group Descriptions			
RandAll NG		Data Displays for Reporting	
Code	Description	Description	Order ^[1]
G	GSK3772847 10 mg/kg	GSK3772847	2
P	Placebo	Placebo	1

NOTES:

[1] Order represents treatments being presented in TFL, as appropriate

Treatment comparisons will be displayed as follows using the descriptors as specified:

- GSK3772847 vs Placebo

5.2. Baseline Definitions

For all endpoints (except as noted in baseline definitions) the baseline value will be the latest pre-dose assessment with a non-missing value, including those from unscheduled visits. If time is not collected, Day 1 assessments are assumed to be taken prior to first dose and used as baseline.

Parameter	Study Assessments Considered as Baseline			Baseline Used in Data Display
	Screening	Run-in	Day 1 (Pre-Dose)	
Primary Endpoints				
Fractional Exhaled Nitric Oxide (FeNO)	X		X	Day 1
Blood Eosinophils	X		X	Day 1
Other Patient Reported Outcomes				
AQLQ			X	Day 1
Asthma Control Questionnaire (ACQ-5) score	X		X	Day 1
Spirometry				
Forced Expiratory Volume (FEV1)	X		X	Day 1
Pharmacodynamics				
Free and total sST2 (serum)			X	Day 1

Parameter	Study Assessments Considered as Baseline			Baseline Used in Data Display
	Screening	Run-in	Day 1 (Pre-Dose)	
Safety				
Vital Signs	X	X	X	Day 1
12-lead Electrocardiogram (ECG) measurements	X		X	Day 1
24 hours Holter measurements		X	X	Day 1
Clinical laboratory tests (haematology and chemistry)	X		X	Day 1
Immunogenicity: Anti-GSK3772847 antibodies			X	Day 1
Biomarkers				
Induced sputum biomarkers		X	X	Run-in ¹
Exploratory serum markers (including IgE and Fungal-specific IgE)	X		X	Day 1

NOTES:

- Unless otherwise stated, the mean of replicate assessments taken on the same day will be used as the value for that day.
- ¹ Baseline is taken at run-in. If the sputum taken at run-in is not viable then a sample is taken at Day 1 (Pre-Dose) and is used as baseline.

5.3. Multicentre Studies

In this multicentre global study, enrolment will be presented by investigative site and country.

5.4. Examination of Covariates, Other Strata and Subgroups

No analysis will be performed on this data due to low subject numbers.

5.5. Multiple Comparisons and Multiplicity

No adjustment for multiplicity is required for this study, as no analysis will be performed.

5.6. Other Considerations for Data Analyses and Data Handling Conventions

Other considerations for data analyses and data handling conventions are outlined in the appendices:

Section	Component
12.3	Appendix 3: Assessment Windows
12.4	Appendix 4: Study Phases and Treatment Emergent Adverse Events
12.5	Appendix 5: Data Display Standards & Handling Conventions
12.6	Appendix 6: Derived and Transformed Data
12.7	Appendix 7: Reporting Standards for Missing Data
12.8	Appendix 8: Values of Potential Clinical Importance

6. STUDY POPULATION ANALYSES

6.1. Overview of Planned Study Population Analyses

The study population summaries will be based on the modified intent to treat population (mITT), unless specified to be on the All Subjects Enrolled (ASE) population.

Study population summaries including subject's disposition, protocol deviations, demographic and baseline characteristics, prior and concomitant medications, exposure and treatment compliance will be based on GSK Core Data Standards. Details of the planned displays are presented in [Appendix 10](#): List of Data Displays.

